### 5.3 Method for Assigning Subjects to Treatment Groups

All subjects will receive the same drug protocol in an open label fashion—there will be no blinding or placebo.

## **5.5 Subject Compliance Monitoring**

We will monitor participants' compliance through self-report and by counting the remaining pills at person visits.

## **5.6 Prior and Concomitant Therapy**

Women are required to be free of any medications that influence ovarian hormones or are contraindicated for use with the study medications; however, prior medication usage will not preclude participation in the study.

## **5.7 Packaging**

The UNC Investigational Drug Service will receive the active drug from their Pharmacy storeroom.

## **5.8 Blinding of Study Drug (if applicable)**

N/A

## **5.9 Receiving, Storage, Dispensing and Return**

The UNC Investigational Drug Service will receive the study drugs from the UNC Pharmacy Storeroom and will dispense the drug to the research coordinator to deliver to participants. Any unused drug will be returned to the UNC Investigational Drug Service.

### **5.9.1 Receipt of Drug Supplies**

The research coordinator will be primarily responsible for picking up the prescription from IDS. Upon receipt, the coordinator will check the pill bottle to ensure the prescription is for the correct participant.

### **5.9.2 Storage**

Medication will be stored at 20° to 25° C in a temperature-controlled facility.

### **5.9.3 Dispensing of Study Drug**

Drugs will be dispensed in tight, light-resistant containers and defined in the USP, with a child-resistant closure.

### **5.9.4 Return or Destruction of Study Drug**

At the completion of the study, there will be a final reconciliation of drug shipped, drug consumed, and drug remaining. This reconciliation will be logged on the drug reconciliation form, signed and dated. Any discrepancies noted will be investigated, resolved, and documented prior to return or destruction of unused study drug. Drug destroyed on site will be documented in the study files.

# 6 Study Procedures

**Overview.** This single-site study will include 4 primary study visits and the OC administration (**Figure 2**). The experimental protocol will last 12-weeks and the entire study will last approximately 4-months with a single follow-up assessment. Participants will undergo screening and consent (T0), a baseline assessment (T1), testing at the end of OC administration (T2), brief testing monthly to examine side effects and protocol adherence, and a follow-up assessment one month post-intervention (T3). Participants will complete fMRI imaging and self-report questionnaires prior to OC administration and at the end of OC administration: T1 and T2. At the completion of the study and after T3, subjects will be given the option to meet with the study PI and discuss whether their ED symptoms changed during OC administration.

The study timeline is depicted in **Figure 2** in Section 3, and the primary procedures that will take place are outlined in **Table 2** and detailed below.

**Table 2: Study Visit Procedures**

Primary Study Procedures					
Procedure	T0	T1	T2	T3	Monthly Visit
Informed Consent	x				
Clinical Health Interview	x				
Venipuncture	x				x
Side Effects and Adherence			x		x
Self-report Questionnaires					
Demographics	x				
EPSI	x	x	x	x	x
BIS/BAS		x	x	x	
SPSRQ		x	x	x	
Kirby Delay Discounting Questionnaire		x	x	x	
fMRI Tasks					
MIDT		x	x		

Participants. Women between the ages of 18-34 with a normal weight binge-eating syndrome. All participants will undergo the same drug protocol in an open label manner.

OC Administration. Participants will begin taking OC for 84 days (i.e., 12-weeks) continuously on the first day of their period after T1. During the final two weeks of OC administration, T1 assessments will be repeated (T2).

Clinical Assessments. Specific study procedures, measures used to obtain primary and secondary outcomes, and the assessment schedule for the protocol are shown in **Table 2**. All study measures are empirically valid and reliable. The focus of this pilot study is on the primary outcomes of binge eating and brain activation in response to reward examined via fMRI.

## Clinical Interviews

SCID-5: Structured Clinical Interview for DSM-5 will be administered by trained study staff at T0, and supervised by [name], to confirm eligibility and assess lifetime comorbid psychiatric diagnoses. The ED module of the SCID-5 will be repeated at T2.

## Self-report Questionnaires

Self-report questionnaires will be completed through secure, encrypted, online survey (i.e., Qualtrics), and scored by standard conventions. Primary and secondary outcome measures are bolded. Some measures are included to overlap an anticipated protocol for a larger study based off of these pilot data and due to previous studies showing they may be related to ovarian hormone sensitivity (i.e., they may predict who is sensitive to changing hormones); however, these measures will not be examined as outcomes in the current study. A long term goal of this line of work is to develop models to predict sensitivity to ovarian hormone fluctuations.

- a) Demographics: at baseline, subjects will be asked to self-report relevant demographic information in order to address eligibility and to characterize the sample: age, race, ethnicity, marital status, and education level.
- b) Life Events Checklist: will be completed at baseline only to obtain information on the number of adverse life events experienced by the participant. Previous studies have suggested that ovarian hormone sensitivity is greater in women with a history of adverse life events. It will be included in the larger mechanistic trial.
- c) UPPS-P Impulsive Behavior Scale: The UPPS-P Impulsive Behavior Scale is a 59-item self-report questionnaire that assesses distinct dimensions of impulsivity. Here we include the negative urgency, lack of premeditation, and sensation seeking subscales. It will be completed at baseline only and be included in the larger mechanistic trial.
- d) Inventory of Depression and Anxiety Symptoms (IDAS): is a 64-item questionnaire that comprehensively assesses anxiety and depression symptoms, including ill temper, dysphoria, panic, social anxiety, appetite change, lassitude, well-being, suicidality, traumatic intrusions, and insomnia. The full IDAS will be given at T0. The dysphoria, suicidality, appetite, and well-being subscales will be given at the monthly visits to monitor subject safety.
- e) Eating Disorder Examination Questionnaire (EDEQ): The EDEQ is a self-report measure of ED symptoms. The EDEQ will be used as a distinct assessment measure to monitor subject safety at the monthly visits.
- f) Eating Pathology Inventory (EPSI): The EPSI is a 45-item self-report questionnaire assessing various aspects of eating disorder symptomatology and will be included in order to obtain a more detailed examination of symptoms compared with frequency counts only. The EPSI includes eight subscales; however, we only include the following subscales in the current project: binge eating, body dissatisfaction, cognitive restraint, purging, excessive exercise, and restricting. A majority of the previous studies to date examining symptom change over the menstrual cycle have focused on symptom-scores, including pilot data from our own group using the EPSI.
- g) Three-Factor Eating Questionnaire-Hunger (TFEQ-Hunger) Subscale: The TFEQ-Hunger subscale will be used to assess self-reported hunger. It will be included in the larger mechanistic trial.
- h) EEI: The Eating Expectancies Inventory (EEI) will be given at T1. The EEI measures learned expectations about eating and contains five subscales. We include the eating helps manage negative affect, eating is useful as a reward, and eating leads to feeling out of control subscales. It will be included in the larger mechanistic trial.
- i) Perceived Stress Scale (PSS): The PSS is a 10-item measure of general stress. It measures the degree to which situations in one's life are perceived as stressful. It measures perceived stress over the past month. It will be completed at T1 and addressed as a potential predictor of hormone sensitivity in the larger mechanistic trial.
- j) Behavioral Inhibition/Behavioral Activation Scales (BIS/BAS): The BIS/BAS Scales is a 24-item measure designed to measure behavioral inhibition and behavioral activation. It is comprised of four subscales: BIS, Reward Responsiveness, Drive, and Fun Seeking, and 20 items total that assess behavioral inhibition and behavioral activation. Primary outcome of interest is the behavioral inhibition subscale. The BIS/BAS scales are associated with neural markers of psychopathology.
- k) Sensitivity to Punishment/Sensitivity to Reward Questionnaire (SPSRQ): The SPSRQ is a 48-item self-report questionnaire used to assess sensitivity to reward and sensitivity to punishment. Primary outcome of interest is the sensitivity to reward subscale.
- l) Kirby Delay Discounting Questionnaire: is a measure of temporal discounting. Participants complete a series of 27 questions that each require choosing between a smaller, immediate monetary reward today versus a larger reward later. An individual's rate of delay discounting is quantified using a hyperbolic discounting function:

$$V = A/(1 + kD),$$

where  $V$  is the present value of the delayed reward  $A$  at delay  $D$ , and  $k$  is a free parameter that determines the discount rate. The higher one's discount rate ( $k$ ) is, the more they discount larger future rewards. An example of applying this formula: ("\\$31 today" or "\\$85 in 7 days"), where  $V = \$31$ ,  $A = \$85$ , and  $D = 7$ . Solving for  $k$  generates the listed  $k$  value of .25. Syntax has been created to calculate the  $k$  parameter from questionnaire responses.

Scoring for Primary and Secondary Outcomes Self-report Questionnaires			
Scale	Likert Scale	Minimum Score	Maximum Score
EPSI	5 point		
Binge eating		0	32
BIS/BAS	4 point		
Behavioral inhibition		7	28
SPSRQ	2 point(T/F)		
Sensitivity to reward		0	24

## **Functional MRI**

The following task, along with a resting scan, will be included in each of the two, one hour-long fMRI sessions:

- a) **Monetary Incentive Delay Task (MIDT)**: Two event-related MID runs consist of 6-second trials during which women will be presented with a cue shape, a fixation crosshair (for variable duration), the target, and performance (win/loss/neutral) feedback. Cues indicate whether it is an incentive (gain, loss) or non-incentive trial. In incentive trials, women can gain or lose money by pressing a button during target presentation; difficulty is based on individual reaction times. MIDT defines reward response as the average speed of responses to reward vs. non-reward trials during a reward task. The MIDT will be completed in the fMRI scanner. A resting state fMRI will also be completed.
- b) **Positive Affect Negative Affect Schedule**: The PANAS is a 10-item questionnaire that measures current positive and negative affect. The measure will be given to subjects prior to the fMRI task.
- c) **Food Intake**: We will ask women to self-report their food intake prior to fMRI. Detailed information will be obtained so that estimated caloric intakes can be determined based on the provided information as well as the number of meals and snacks eaten.

## **FMRI Data Acquisition and Image Processing:**

Scanning is performed using a Siemens Prisma scanner at the UNC BRIC. High-resolution, T1-weighted anatomical images will be acquired using an MPRAGE sequence. Whole-brain functional images will be acquired using a single-shot, gradient recalled echoplanar pulse sequence sensitive to blood-oxygen-level-dependent (BOLD) contrast. Each of 2 runs will consist of the acquisition of 195 successive brain volumes. fMRI image preprocessing, processing, and analysis will be conducted using FSL and custom MATLAB scripts. fMRI analyses will include an event-related BOLD response analysis within a priori ROI. Contrasts of interest will include win vs. non-win outcomes. [name] will be responsible for fMRI data acquisition and initial imaging processing and provide the data to [name] for analysis.

## **Daily and Weekly Symptom Assessment**

- a) **Daily/Weekly Rating Form**: We created a survey for daily and weekly assessment of symptoms based off of the 20-item DSRP and the 6-item Short Evaluation of Eating Disorders (SEED). The DSRP was designed to assess the presence and intensity of physical and mood symptoms that

accompany ovarian hormone changes whereas the SEED was developed to monitor ED symptom change. Generally, these measures were combined in order to address ED symptoms and physical/mood symptoms. Prior to OC administration, subjects will complete this monitoring form daily in order to capture symptoms during a natural menstrual cycle. During OC administration, participants will complete this form weekly. **During medication administration, ratings will be transmitted to the study team in real-time to monitor safety.**

#### Assessment Schedule.

**Eligibility.** Interested participants will initially complete an online screening survey to assess potential eligibility. No more information than required to determine an accurate representation of eligibility will be collected. This can also be completed by telephone interview if needed. Women who screen eligible on the survey and are interested in participating in the study will be contacted by a member of the study staff to schedule a screening assessment to confirm eligibility and review consent. This is done in order to decrease participant burden (having clearly ineligible individuals complete an in-person screening).

**Screening (T0).** At this initial screening visit (T0), consent forms will be reviewed, eligibility confirmed, and clinical interview completed. A Clinical Health Screening will be completed to examine inclusion/exclusion criteria. For those participants who appear eligible, blood will also be drawn and a pregnancy test completed prior to enrollment. Similar to our previous studies, this will include a laboratory panel (CMP) and cholesterol. Prior to final enrollment, the investigative team will review the findings of the Clinical Screening to determine appropriateness and eligibility for the study.

After enrollment, participants will complete the Daily Symptom Assessment for one menstrual cycle. This form will be completed each morning and ask questions about the previous day. We expect the completion of the Daily Symptom Assessment to take no longer than 5 minutes. During the screening period, participants will also be given ovulation test kits to use in home. This will pinpoint when during the subject's menstrual cycle ovulation occurs, so that the mid-luteal phase can be determined (see below for more details).

**Baseline (T1).** Prior to beginning OC administration, participants will complete a baseline assessment including self-report questionnaires. The baseline fMRI will also occur at this visit. This visit will be scheduled during the mid-luteal phase of the subject's menstrual cycle as this is when symptoms are expected to be at their "worst." The mid-luteal phase will be determine via the ovulation test kits provided to each subject. Beginning with OC administration, subjects will begin the Weekly Symptom Assessment (similar to the Daily Assessment but completed Weekly). Based on anticipated risk-benefit ratio and participant burden, we have subjects complete this form only weekly during medication administration. Given side effects for OCs are expected to be relatively minimal (if present at all), having subjects complete this form daily for 12-weeks would represent significant and unnecessary participant burden.

**End-of-OC administration (T2).** During the last two weeks of OC administration, participants will repeat the study procedures from T1, including fMRI.

**Side Effects.** Two check-ins with study staff will occur during the 84 day OC administration period—approximately 4-weeks after OC administration begins and approximately 8-weeks after OC administration begins (i.e., monthly). During these check-ins, side effects and protocol adherence will be monitored. During the first check-in visit (4-weeks post-OC administration), a basic metabolic panel will be redrawn.

**Follow-up (T3).** One month after study completion, a brief online follow-up assessment will be completed by participants to assess symptoms after discontinuation of study medications. At the completion of the study and after T3, subjects will be given the option to meet with the study PI and discuss whether their ED symptoms changed during OC administration.

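### T3, the only assessment after the drug is stopped, names no mood, suicidality or side-effect measure, so about 4 weeks pass with none solicited

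*Combined protocol and SAP*

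**What the plan says.** Section 3.1 places T3 one month after the intervention. Section 6 (Assessment Schedule, Follow-up) gives its purpose: "a brief online follow-up assessment will be completed by participants to assess symptoms after discontinuation of study medications". That paragraph lists no instruments, and neither does the COVID version of T3 in Appendix B.

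The rest of Section 6 fixes when each candidate measure is given:

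- **Table 2** marks EPSI, BIS/BAS, SPSRQ and the Kirby questionnaire at T3. Its row "Side Effects and Adherence" is marked at T2 and the monthly visits and is blank at T3.
- **EPSI** covers eating pathology only: "we only include the following subscales in the current project: binge eating, body dissatisfaction, cognitive restraint, purging, excessive exercise, and restricting".
- **IDAS** is given in full at T0. After that, "The dysphoria, suicidality, appetite, and well-being subscales will be given at the monthly visits to monitor subject safety". The Side Effects paragraph puts the two check-ins at about 4 and 8 weeks of dosing. The EDEQ is also used for safety at those visits.
- **PANAS** is tied to the scans: "The measure will be given to subjects prior to the fMRI task". Scans take place at T1 and T2.
- **The rating form** draws on two scales, one of which is described thus: "The DSRP was designed to assess the presence and intensity of physical and mood symptoms". Its schedule on treatment is: "During OC administration, participants will complete this form weekly". Section 9.3 pays for 12 weekly forms.

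Section 4.4.1 attaches two safeguards to the weekly form: staff are alerted at once when a woman reports active risk or severe adverse effects, and a missed form leads to a phone safety assessment. The same section makes the principal investigator responsible for documenting, investigating and following up all study-related adverse events.

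**The concern.** T3 exists to find out what happens after the drug is stopped, but the instruments marked for it cover eating pathology, reward sensitivity, inhibition and delay discounting. None asks about mood, suicidality or physical side effects. The alert and the missed-form call belong to the weekly form, so they have no stated application once dosing ends.

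The protocol itself treats mood as a safety matter. It excludes women with a previous suicide attempt, withdraws women judged at elevated suicide risk, lists depression among the rare serious reactions to the drug, and notes that the drug is approved for PMDD. It has women complete the rating form daily during the natural cycle before treatment, but does not schedule that form when treatment, and with it the suppression of ovulation, ends.

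At stake is the detection of new or worsening mood or physical events in the month after the last pill. No effect estimate is at stake. A larger trial that reused this schedule would have eating and reward data after treatment, but no solicited mood or side-effect data.

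**Working it through.** **Inputs.** Dosing lasts 84 days (Section 5.2). Check-ins fall at about weeks 4 and 8 (Section 6). T2 falls in the last two weeks of dosing, weeks 10 to 12 (Section 6). Twelve weekly forms are planned (Section 9.3). T3 is one month post-intervention, and the study is described as 16 weeks long (Section 3.1). Weeks are counted from the first pill.

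**The plan's own figure.** With one month taken as 28 to 31 days, T3 falls at day 84 + 28 = 112 to 84 + 31 = 115. Dividing by 7 gives week 16.0 to 16.4, which reproduces the stated 16 weeks.

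**Time from the last scheduled use of each measure to T3** (T3 taken as week 16):

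| Measure | Last scheduled | Gap to T3 |
|---|---|---|
| Weekly form (mood, eating, side effects, alerts) | about week 12 | 16 − 12 = 4 weeks |
| Side-effects and adherence check | T2, weeks 10 to 12 | 16 − 12 = 4 to 16 − 10 = 6 weeks |
| PANAS | T2, weeks 10 to 12 | 4 to 6 weeks |
| IDAS suicidality and other safety subscales | about week 8 | 16 − 8 = 8 weeks |

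With a 31-day month, the gap from the weekly form is 31/7 = 4.4 weeks and the gap from the IDAS is (115 − 56)/7 = 8.4 weeks.

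**Reading the gaps together.** The 8 weeks since the last IDAS subscale split into 12 − 8 = 4 weeks on drug, when the weekly form and its alerts are running, and 16 − 12 = 4 weeks off drug, when nothing named is running. The interval without any named mood, suicidality or side-effect measure is therefore about 4 weeks, and T3 at its end does not close it. The number of such measures named after the last pill is 0.

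**Sensitivity to the start of the month.** Section 6 counts T3 from study completion, which is less definite than Section 3.1. If a 28-day month were counted from the T2 visit, T3 would fall at weeks 10 + 4 = 14 to 12 + 4 = 16. The gap from the last pill would then be 2 to 4 weeks, and from the last IDAS subscale 6 to 8 weeks. T3 would still contain no named safety measure.

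**The case against.** The best reply is that this argues from silence. Table 2 lists primary procedures only and leaves out the IDAS, EDEQ, PANAS and rating form, all of which the text does schedule. A blank at T3 therefore proves little by itself. The T3 sentence speaks of symptoms without listing instruments, and elsewhere in Section 6 that word covers mood and physical complaints as well as eating. Figure 2 is not visible. This stands in part: T3 may simply be under-described. But the text gives the timing of every relevant measure, and none is placed at T3, so staff following the plan as written would not collect them.

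Several stronger readings are tempting, and the documents do not support them:

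- *Eight weeks without monitoring.* That figure belongs to the IDAS alone. The weekly form, with alerts, covers weeks 8 to 12, and side effects are checked at T2.
- *T3 is the only off-drug assessment.* T0, T1 and the daily ratings also come before any drug. T3 is the only one after it.
- *The natural cycle returns within the T3 month.* Section 1.5 says menses resumes within 60 days for 95% of women, about twice the interval to T3. Some women may not have cycled by then, and a single T3 form could miss a later change.
- *The protocol shows mood worsening after stopping.* It does not. The hormone-free-week argument in Section 1.1 explains incomplete response of bulimia symptoms on a 21/7 regimen, and EPSI measures eating symptoms at T3. Extending the argument to mood is an inference.
- *The adverse-event duty lapses at the last pill.* Section 4.4.1 sets no such limit. It is a duty to handle events, though, and it does not ask women about them.
- *The results are compromised.* The planned tests of the primary and secondary outcomes compare T1 with T2, and none uses T3.

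Two further points count against a high rating. Women with a previous suicide attempt, bipolar disorder or psychotic episodes are excluded, as are those judged at elevated suicide risk at enrollment. Recruitment has also been terminated, so few women, possibly none, have yet to reach T3.

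**Conclusion.** The point holds as a minor safety improvement. Followed as written, the plan solicits no mood, suicidality or side-effect data after the last pill: about 4 weeks per woman, T3 included, or 2 to 4 weeks if T3 is counted from T2. New events in that time would be found only if a woman reported them unprompted, or raised them at the optional meeting after T3, which is offered to discuss her response to the drug and is not described as a safety assessment.

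This rests on reading T3 as containing only what the visible text names, and on one month being about 4 weeks from the last pill. The documents give no rate of mood or physical events after stopping, so no expected number of missed events can be stated. If the T3 form already includes such items, all that is left is to name them in the protocol.

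**What to change.** Add two existing sets of items to the online T3 form: the side-effect items, and the four IDAS subscales used at the monthly visits (dysphoria, suicidality, appetite, well-being). Mark both at T3 in Table 2. State that the Section 4.4.1 process applies to T3: immediate staff notification when risk is endorsed, and a phone safety contact when the form is not returned. Optionally, give the same four subscales at T2, so that the T3 scores have an end-of-dosing value to compare with.

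The cost is a few minutes per woman at an existing online timepoint, staff time to review alerts and chase missed forms (some alerts will be false alarms), and a small IRB amendment. No new visit is needed. If the remaining participants have already passed T3, apply the change to any larger trial that reuses this schedule.
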